Day 1 and every 21 days: Ipilimumab therapy at 3 mg/kg as a 90 minute intravenous (IV) dose and BMS-986156 (dose as determined in group 1) as a 60 min IV will be given in an outpatient setting. Dose cycles will be repeated every 21 days: on days 1, 22, 43, and 64 for a total of 4 cycles. Nivolumab (480 mg Q4W) will start day 85 and continue every 28 days for 26 cycles. Enrollment of this group will start based on the following criteria. If 2 out of 6 patients, or less, display DLTs, then, enrollment of group 2 can begin. Alternatively, if 3 out of 6 patients, or more, display DLTs, then, enrollment of group 2 cannot begin until 10 patients have been treated in group 1.

SBRT: SBRT will be given after 2 doses of ipilimumab and BMS-986156 on days 29-32 for 50 Gy in 4 fractions or on days 29-40 for 60 Gy in 10 fractions (no SBRT during weekends): SBRT will be directed at 1-4 targetable liver or lung lesion(s). To minimize treatment breaks, patients may start radiation on a Monday.

Group 2

[figure not shown]

Diagram of Treatment Schedule for Ipilimumab + BMS-986156 x 2 → SBRT → Ipilimumab + BMS-986156 x 2 → Nivolumab x 26 (Treatment group 2).

Group 3, 20 patients: Nivolumab + BMS-986156 x 1 + SBRT → Nivolumab + BMS-986156 x 3 → Nivolumab x 22

First dose of Nivolumab + BMS-986156 and SBRT will be given concurrently (early) and followed by Nivolumab + BMS-986156 x 3; then, Nivolumab monotherapy for 22 cycles. Nivolumab will be administered for a total of 26 cycles, either as a combination or monotherapy, in this group. Enrollment of patients for this group will start around the same time as group 1. Choice of treatment group will be at the discretion of PI and treating physician.

Nivolumab therapy at 480 mg dose will be given on day 1 as a 30 minute IV dose and BMS-986156 at 30 mg dose will be given on day 1, 29, 57, 85 as a 60 min IV in an outpatient setting. Nivolumab monotherapy will start on day 113 and will continue for 22 cycles.

SBRT: SBRT will be given on days 1-4 (days 2-5 are acceptable if scheduling does not permit radiation to begin same day as infusions) for 50 Gy in 4 fractions or on days 1-12 for 60 Gy in 10 fractions (no SBRT during weekends). SBRT will be directed at 1-4 targetable liver or lung lesion(s). To minimize treatment breaks, patients may start radiation on a Monday.

Group 3

[figure not shown]

Diagram of Treatment Schedule for Nivolumab + BMS-986156 x 1 + SBRT → Nivolumab + BMS-986156 x 3 → Nivolumab x 22 (Treatment group 3)

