Efficacy data from Phase I and II studies in melanoma suggest a trend of increasing durability and progression free survival (PFS) rates with increasing doses and duration of exposure to ipilimumab. However, preliminary data suggests that 10mg/kg of ipilimumab is associated with a higher frequency of SAEs and serious (Grade 3 or higher) irAEs than 3mg/kg of ipilimumab(2, 11, 12). It appears that an increased awareness and better management of these side effects has led to a decrease in their severity and an improvement in their control in recent trials. We propose to use ipilimumab at 3 mg/kg dose administered as 4 doses every 3 weeks and will implement a tight safety rule (see section 7.3) to stop the trial in case of excess toxicity.

It is important to note that because ipilimumab works indirectly through stimulation of the immune system by enhancing T-cell activation, its effect on tumor burden may take weeks to months to become apparent. The clinical activity of ipilimumab may manifest, not only as an early objective response, but also as stable disease (SD) with slow, continuous decline of tumor burden toward response and, in some cases, as a late objective response after initial tumor volume increase (12). For example, in one study (MDX010-19) the time to first response ranged from day 40 to day 441 (10). Durable responses and SD after treatment with ipilimumab have been observed in several malignancies, including melanoma, prostate and renal cell carcinoma.

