7.1.1.2 Group 2: Dose De-Escalation of BMS-986156 when combined with ipilimumab plus SBRT

BMS-986156 dose as determined in group 1, for combination treatment with ipilimumab, before adding SBRT to the treatment regimen.

Treatment group 2: A modified 3+3 dose de-escalation then expansion to a total of 20 patients will occur at the MTD.

The first 3 subjects will be enrolled at dose level 1 (3 mg/kg ipilimumab + BMS-986156).

- If 0 out of these 3 patients have a DLT, 3 additional patients will then be enrolled on this same dose level.
- If 1 of 3 subjects have a DLT, 3 more patients will then be enrolled at this dose level. If only 1 of the 6 total subjects at dose level has a DLT, then this dose level will be considered safe and all other patient in this arm will be treated at this dose level.
- If 2 of 6 subject have DLT at dose level 1, then the dose will be de-escalated as per table below.
- If 2 of 3 subjects have a DLT at dose level 1, then the dose will be de-escalated as per table below

Dose De-Escalation of Ipilimumab when combining with BMS-986156 plus SBRT.

If MTD from group 1 finds the 30mg BMS-986156 then:

Dose Level 1 3 mg/kg Ipilimumab + 30 mg BMS-986156

Dose Level -1 1 mg/kg Ipilimumab + 30 mg BMS-986156

If MTD from group 1 finds the 100mg BMS-986156 then:

Dose Level 1	3 mg/kg Ipilimumab + 100 mg BMS-986156
Dose Level -1	1 mg/kg Ipilimumab + 100 mg BMS-986156
Dose Level -2	1 mg/kg Ipilimumab + 30 mg BMS-986156

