 - If 1 of 3 subjects have a DLT in dose level, 3 more patients will then be enrolled at this dose level. If only 1 of the 6 total subjects at dose level has a DLT, then this dose level will be considered safe and all other patient in this arm will be treated at this dose level.
 - If 2 of 6 subject has DLT then the dose will be de-escalated as per table below.
 - If 2 of 3 subjects have a DLT at dose level 1, then the dose will be de-escalated as per table below

Dose De-Escalation of BMS-986156 when combining with Nivolumab plus SBRT.

Dose Level 1	480mg Nivolumab + 30 mg BMS-986156
---------------------	------------------------------------

Dose Level -1 480mg Nivolumab + 10 mg BMS-986156**7.1.2. Reinduction for all arms**

Reinduction will be allowed for patients in which the treating physician feels there was benefit from the trial treatment. It will consist of repeating the original treatment using the same schedule for each arm. Radiation may be given during reinduction, but is not required. Pending the treating radiation oncologist judgment, additional radiation therapy to a previously non-irradiated lesion can be administered during re-induction. Timing of radiation during reinduction will be at the discretion of treating Radiation Oncologist.

The target lesion for radiation will be chosen by the treating radiation oncologist. The target lesion must not have been previously irradiated. The target lesion does not have to be within the same organ that was initially treated during the initial treatment (e.g. patients who received initial lung lesion irradiation can have liver or a bone lesion irradiated during re-induction). Radiation dose and fraction will be either at the initial dose (50 Gy in 4 fractions or 60 Gy in 10 fractions) or at a lower palliation dose (30 Gy in 10 fractions) and may also be combined with low dose radiation ranging from 200cGy-1000cGy in multiple fractions, at the discretion of the treating radiation oncologist.

Other tumor sites may be treated for palliation concurrently or sequentially if needed at the discretion of the treating radiation oncologist.

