- Any clinically ≥ grade 3 non-hematologic toxicity as defined in the NCI CTC v4.0, expected and believed to be related to the combination of study drug and radiation (except nausea and vomiting, diarrhea and electrolyte imbalances responsive to appropriate regimens, alopecia or fatigue lasting less than 7 days).
- Grade 3 Febrile neutropenia
- Any grade 4 neutropenia (with or without fever and/or sepsis) or thrombocytopenia (without bleeding) lasting at least 1 week or longer (as defined by the NCI-CTC v4.0).
- Any of the Grade 4 hematologic adverse events for >7 days.
- Any ≥ grade 3 nausea or vomiting lasting > 5 days despite anti-emetics regimens or ≥ grade 3 diarrhea refractory to anti-diarrhea medications, >48 h.
- Any Grade 2 drug-related uveitis or eye pain or blurred vision that does not respond to topical therapy and does not improve to Grade 1 severity ≤2 weeks OR requires systemic treatment. Any other grade 3 non-hematologic toxicity including symptoms/signs of vascular leak or cytokine release syndrome; or any severe or life-threatening complication or abnormality not defined in the NCI-CTCAE v4.0 that is attributable to the therapy, with the following EXCEPTIONS:
 - Grade 3 or grade 4 electrolyte abnormalities that are not complicated by associated clinical adverse experiences, last ≤48 hours and either resolve spontaneously or respond to conventional medical intervention
 - Isolated Grade 3 elevation of amylase or lipase not associated with clinical or radiographic evidence of pancreatitis
 - Isolated Grade 3 fever not associated with hemodynamic compromise (eg, hypotension, clinical or laboratory evidence of impaired end-organ perfusion)

- Grade 3 endocrinopathy that is well controlled by hormone replacement
- Grade 3 tumor flare (defined as pain, irritation, or rash that localizes to sites of known or suspected tumor)
- Grade 3 fatigue for ≤ 7 days.
-

Group 2 and Group 3 definition of DLTs:

- DLTs used to define the MTD in combination with radiation section 7.1.1.2 and 7.1.1.3 will only use DLTs associated with organ toxicity for the organ irradiated.
- SBRT related adverse events: Any grade ≥ 3 events occurring in radiation volume field will be considered as DLT.
- Any \geq Grade 3 bronchospasm or other hypersensitivity reactions lasting for > 6 h;

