- Any other \geq Grade 3 non-skin related adverse event with the exception of laboratory abnormalities that is asymptomatic, not requiring hospitalization, responsive to supplementation within 24 hours).
- Any Grade 4 laboratory abnormalities, except AST, ALT, or total bilirubin;
 - AST or ALT $> 8 \times$ ULN,
 - Total bilirubin $> 5 \times$ ULN;
 - AST or ALT $> 3 \times$ ULN AND Total Bilirubin $> 2 \times$ ULN (Potential drug-induced liver injury as defined by Hy's Law)
- Grade 3/4 rash if no improvement (i.e. resolution to \leq Grade 1) after a 1-2 week infusion delay. Use of topical steroids is permitted.
- Any other Grade 4 adverse event;
- Any adverse event, laboratory abnormality or intercurrent illness which, in the judgment of the investigator, presents a substantial clinical risk to the subject with continued study drug dosing;
- Any motor neurologic toxicity \geq Grade 3 regardless of causality;
- Any \geq Grade 3 treatment-related sensory neurologic toxicity.
- Combination related toxicity, such as infusion reactions, diarrhea, colitis, etc., that prevents administration of ipilimumab/BMS-986156 for > 21 days and/or nivolumab/BMS-986156 for > 28 days from the scheduled dose.
- Any clinically \geq grade 3 non-hematologic toxicity as defined in the NCI CTC v4.0, expected and believed to be related to the combination of study drug and radiation (except nausea and vomiting, diarrhea and electrolyte imbalances responsive to appropriate regimens, alopecia or fatigue lasting less than 7 days).
- Grade 3 Febrile neutropenia
- Any grade 4 neutropenia (with or without fever and/or sepsis) or thrombocytopenia (without bleeding) lasting at least 1 week or longer (as defined by the NCI-CTC v4.0).

- Any of the Grade 4 hematologic adverse events for >7 days.
- Any ≥ grade 3 nausea or vomiting lasting > 5 days despite anti-emetics regimens or ≥ grade 3 diarrhea refractory to anti-diarrhea medications, >48 h.
- Any Grade 2 drug-related uveitis or eye pain or blurred vision that does not respond to topical therapy and does not improve to Grade 1 severity ≤2 weeks OR requires systemic treatment. Any other grade 3 non-hematologic toxicity including symptoms/signs of vascular leak or cytokine release syndrome; or any severe or life-threatening complication or abnormality not defined in the NCI-CTCAE v4.0 that is attributable to the therapy, with the following EXCEPTIONS:

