10.1. Data Set Descriptions

For group 1, after BMS-986156, dose as determined in group 1, an additional 4 patient expansion per dose level (10 patients total for each dose level) will be enrolled in that group, at the determined dose from group 1, to help determine biological endpoints. Should DLTs occur in more than 33% of patients enrolled into this expanded group, dosing at that level will be stopped. The next lower dose level will be considered the safe dose. A review of all DLTs observed will be conducted, and the need to lower the dose will be based on the discussion and agreement between the IRB and the Investigator.

All patients who receive any ipilimumab, BMS-986156, or nivolumab will be considered evaluable for toxicity.

For toxicity and response: all patients receiving at least 1 (concurrent group) or 2 (sequential group) treatment with trial drugs and completed half of the planned radiation treatment (except for group 1 where no radiation is given) will be considered evaluable for toxicity and response and included in the efficacy data set.

Group 1: (Total of 20 patients: 10 patients with 30 mg and 10 patients with 100 mg of BMS-986156, when combined with ipilimumab at 3mg/kg). Nivolumab (480mg) Q4W monotherapy will be administer for 26 cycles.

Group 2: 20 patients: trial drugs, two doses of ipilimumab (3mg/kg) combined with BMS-986156 (dose as determined in group 1) are given before SBRT. SBRT is given sequentially; followed by 2 more doses of ipilimumab + BMS-986156. Nivolumab (480mg) Q4W monotherapy will be administer for 26 cycles.

Group 3: 20 patients: First dose of trial drugs nivolumab (480 mg) and BMS-986156 (30 mg) are given concurrently with SBRT; followed by 3 doses of nivolumab (480 mg) and BMS-986156 (30 mg). Finally, Nivolumab as monotherapy for 22 cycles. Nivolumab will be administered for a total of 26 cycles in this group.

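### Groups 2 and 3 lower systemic drug doses on irradiated-organ DLTs alone; the other DLTs listed for these groups trigger no numeric cohort rule

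*Combined protocol and SAP*

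**What the plan says.** Section 7.2.1 defines DLTs for groups 2 and 3 under one heading. The first bullet names sections 7.1.1.2 and 7.1.1.3 and states that the DLTs defining the MTD there "will only use DLTs associated with organ toxicity for the organ irradiated". The second makes any Grade 3 or higher event in the radiation field a DLT. The remaining bullets largely repeat the group 1 list, and many have no organ limit: "Any other Grade 4 adverse event", febrile neutropenia, motor and sensory neurologic toxicity, uveitis, and combination toxicity such as colitis that prevents dosing.

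The de-escalation sections speak of a DLT without qualification. For group 2: "If 2 of 6 subject have DLT at dose level 1, then the dose will be de-escalated as per table below". For group 3: "If 2 of 6 subject has DLT then the dose will be de-escalated as per table below". Two of the first three patients also triggers de-escalation in either group.

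The group 2 table is titled "Dose De-Escalation of Ipilimumab when combining with BMS-986156 plus SBRT". It lowers ipilimumab from 3 to 1 mg/kg and, if the starting BMS-986156 dose was 100 mg, then lowers that to 30 mg. The group 3 table lowers BMS-986156 from 30 to 10 mg. Neither table changes SBRT.

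**The concern.** The events that are counted do not match the doses that are changed. The only action available is to reduce a systemic drug, but the count that triggers it is limited to the irradiated organ. A drug toxicity elsewhere in the body can be a DLT by the plan's own list and still have no effect on the cohort's dose.

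The safety of the full combinations with SBRT is a primary objective (section 2.1), and the count in the first 6 patients fixes the dose for the remaining 20 - 6 = 14 in each group. Section 3.3 states that there are no clinical data on the safety of BMS-986156 with ipilimumab, so systemic toxicity is a main unknown in group 2.

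**Working it through.** The plan states no operating characteristics for this rule, so there is no figure to reproduce. The check has three parts.

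**1. Does another rule act on the uncounted DLTs?**

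- Section 10.1: "Should DLTs occur in more than 33% of patients enrolled into this expanded group, dosing at that level will be stopped". The paragraph is introduced as applying to group 1, so it covers only the group 1 expansion.
- Section 3.1.1 says the trial "will implement a tight safety rule (see section 7.3) to stop the trial in case of excess toxicity". Section 7.3 contains criteria for delay, restart, discontinuation and removal of individual patients, and no cohort threshold.
- Section 10 requires a summary to the IND Office after the first 3 evaluable patients and every 3 thereafter in each group. This is a cohort review, but it has no DLT threshold.

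No numeric cohort rule remains for these events in groups 2 and 3.

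**2. Does group 1 close the gap?**

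- The DLT window (section 7.2) is 29 days in group 1 and 43 days in group 2. Group 1 DLT counts therefore give no information on days 30 to 43.
- Section 1 opens group 2 on a lenient condition: "If 2 out of 6 patients, or less, display DLTs, then, enrollment of group 2 can begin". Two of six is an observed rate of 33%.
- Group 3 starts at about the same time as group 1, with different drugs, and has no drug-only run-in in this trial.

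**3. How much can the choice of counted DLTs matter?**

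Three more patients follow 0 or 1 DLT in the first three, so the rule de-escalates exactly when at least 2 of 6 have a counted DLT. For a counted rate p:

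P(de-escalate) = 1 - (1-p)^6 - 6p(1-p)^5

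Example at p = 0.06: 1 - 0.6899 - 0.2642 = 0.0459. The staged calculation gives the same value: P(2 or more of 3) + (1-p)^3 × P(2 or more of 3) + 3p(1-p)^2 × P(1 or more of 3) = 0.0104 + 0.0086 + 0.0269 = 0.0459.

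| Counted rate p | Source | P(2 or more of 6) |
|---|---|---|
| 2% | Liver SBRT, Grade 3 or higher (section 7.5) | 0.6% |
| 7.9% | Lung SBRT toxicity, grade not stated (section 7.5) | 7.6% |
| 6% | DLTs in the earlier ipilimumab plus SBRT trial (section 3.3) | 4.6% |
| 20% | Assumed | 34.5% |
| 34% | Grade 3 treatment-related toxicity in that trial, not a DLT rate (section 3.3) | 66% |

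The first two rows illustrate organ-only counting and the last three full-list counting. The rows come from different patients and definitions, so the 6% row falling below the lung row does not mean that the full list would count fewer events. In the same patients, the full list counts at least as many.

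**Worked case.** Six group 2 patients receive lung SBRT and two develop Grade 4 colitis inside the window. Colitis is not a toxicity of the irradiated lung, so the count is 0 of 6 and 3 mg/kg continues for the other 14. With all listed DLTs counted it is 2 of 6, and the dose becomes 1 mg/kg.

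**The case against.** The best defence is that the restriction is deliberate. Group 1 tests ipilimumab with BMS-986156 first, so group 2 could be meant to isolate what SBRT adds. The non-organ items also have another use: section 7.3.3 bars restart after an event listed in 7.2.1, and section 7.3.4 permanently stops most affected patients. The IND Office sees every third patient. The earlier ipilimumab plus SBRT trial described most of its Grade 3 toxicity as self-limiting and managed as an outpatient, so counting everything could cost efficacy.

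The aim of isolating SBRT is coherent, but separate tabulation achieves it without excluding other DLTs from the dose decision. The other safeguards are real, but none sets a threshold for lowering a cohort's dose. On group 1, section 7.1.1.1 does make 30 mg the MTD if 2 of 6 have DLTs at 100 mg. That still leaves the shorter window and the opening condition in section 1.

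Three stronger readings are tempting, and the documents do not support them.

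- A reader might infer that the plan leaves open which DLTs count. The bullet cites both de-escalation sections and says only, so a literal reading settles it. The unqualified term in 7.1.1.2 and 7.1.1.3 takes its meaning from 7.2.1.
- A reader might infer that everything below that bullet is systemic. The in-field item is local, and the liver-enzyme, bilirubin and bronchospasm items can be toxicities of the irradiated organ.
- A reader might add the pooled Grade 3/4 immune-related rate for ipilimumab (6.3% to 13%, section 5.1.8) to the SBRT rates and take the result as the chance of a DLT. Those are not rates within the DLT window. Median onset of Grade 3 to 5 events is 7 to 9 weeks (section 5.1.9), or days 49 to 63, after the day-43 cut-off. Some such events are also exempt, such as controlled Grade 3 endocrinopathy.

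**Conclusion.** The rule is wrong as written and should be fixed. The finding rests on the text: de-escalation of systemic drugs is tied to irradiated-organ DLTs, and the other DLTs listed for groups 2 and 3 reach no numeric cohort rule. The effect on the chance of de-escalation cannot be pinned down. Full-list counting gives 4.6% to 66% across the rates considered, against 0.6% to 7.6% at the cited local SBRT rates. These figures assume independent patients with a common rate, none includes a BMS-986156 effect, and the 20% is an assumption. They show that the choice can change the decision, not how often it would.

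The weight falls on group 2. In group 3 the practical consequence is probably smaller: the step is only 30 to 10 mg of BMS-986156, and section 3.1.4 reports one DLT among 225 patients given BMS-986156 with nivolumab, at the 800 mg dose.

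**What to change.** Rewrite the first bullet so that every DLT listed for groups 2 and 3 counts toward de-escalation, together with any in-field Grade 3 or higher event. State that in-field organs other than the target are included, for example the esophagus in a lung field, because the present bullet leaves that open. Add one sentence to 7.1.1.2 and one to 7.1.1.3 saying that this is the count used. Tabulate irradiated-organ DLTs separately to show the effect of SBRT.

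The drafting cost is one bullet and two sentences. The real cost is that de-escalation would trigger more often, so more group 2 patients could receive ipilimumab at 1 mg/kg instead of 3 mg/kg, sometimes for toxicity that proves manageable.

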7.3. Duration of Therapy and Criteria for Treatment Delay

7.3.1. Duration of Therapy:

In the absence withholding treatment cycles due to adverse events, study treatment will be continued for the full 4 Ipilimumab/BMS-986156 cycles, followed by 26 cycles of Nivolumab (group 1 and 2). Nivolumab/BMS-986156 will be given for 4 cycles, followed by 22 cycles of Nivolumab (group3). Nivolumab will be given for a total of 26 cycles on all groups.

7.3.2. Criteria for Treatment Delay:

Patients will delay treatment with ipilimumab/BMS-986156 or nivolumab/BMS-986156 if they experience at least one of the following adverse events considered by the Investigator to be “possibly”, “probably” or “certainly” related to trial drug treatment with or without SBRT treatment:

- Any Grade 3 non-skin related adverse event (excluding alopecia, and Grade 3 nausea, vomiting, and diarrhea for which adequate supportive therapy has been instituted)
- Any Grade 3 skin-related adverse event (including irAEs)
- Any of the Grade 4 hematologic adverse events for >7 days
- Grade 3 fatigue only if ≥ 7 days
- SBRT scheduling conflicts or machine maintenance issues

7.3.3. Criteria for Restart of Ipilimumab/BMS-986156 or nivolumab/BMS-986156 Treatments:

Patients requiring delay or cessation of treatments of trial drugs based on the judgment of the attending physician can be restarted as long as:

- The adverse event is not listed in 7.2.1, and:

- If the adverse event has resolved to \leq Grade 1 severity or returns to baseline within 4 weeks (28 days) of dose administration, treatment will be restarted \geq 4 weeks from the last dose administration, to complete dosing regimen outlined above.
- If the adverse event has not resolved to \leq Grade 1 severity or returned to baseline in the protocol-specified dosing window (3 weeks, for ipilimumab/BMS-986156; 4 weeks for nivolumab/BMS-986156), the next scheduled dose will be omitted and remaining doses will be administered if approved by the Principal Investigator.
- For ipilimumab/BMS-986156: Treatment delays for reasons other than adverse events (e.g. for scheduling conflicts or SBRT machine maintenance issues) are allowed as long as all four 3 week cycle ipilimumab/BMS-986156 doses are given within 8 months. In this scenario, all 4 doses should be administered separated by a minimum interval of 3 weeks.
- For nivolumab/BMS-986156: Extensions to the period of dose delays may be granted for individual subjects on a case by case basis decided by the Investigator in settings where benefit/risk may justify continued study therapy (e.g., subject deriving clinical benefit who requires prolonged steroid taper for management of non-DLT drug-related AEs, or experiences delays for management of a non-drug related AE).
- The end of cycle tumor assessments (i.e., CT/MRI, positron emission tomography, etc) will continue on an every 8 weeks schedule relative to the subject's 1st dose regardless of any treatment delay incurred.

